7.6 Study Conduct

7.6.1 Schedule of Observations

This PMOS will be a single-arm, multi-center, prospective cohort study.

Non-interventional studies are one of several methodical instruments to collect information on drugs available on the market. Their defining characteristic is the lack of influence on the relationship between individual physicians and patients in respect to determining indication as well as choice and conduct of the treatment, while at the same time allowing for the structured and systematic collection of treatment data (see also Section 6 “Rationale”). Adalimumab must not be prescribed for the purpose of including a patient in this PMOS.

Patients will be informed about the type of therapy, alternate therapies, and risks, and they have to provide informed consent before the start of adalimumab therapy. Before enrollment in the PMOS, the patients will be made anonymous. AbbVie GK will only receive access to anonymous data. AbbVie GK can only identify the patients via their patient number.

The documentation consists of patient self-assessments as well as assessments by the physician. The following table provides an overview of the study visits with corresponding study activities (Table 1 “Study Schedule”).

Table 1. Study Schedule

Activity	Visit (Week)					
	0	12	24	52	76	104*
Patient Background	✓					
Inclusion / Exclusion criteria	✓					
Previous RA therapies	✓					
Concomitant diseases and therapies	✓	✓	✓	✓	✓	✓
Current adalimumab therapy	✓	✓	✓	✓	✓	✓
Current RA therapies	✓	✓	✓	✓	✓	✓
Effectiveness						
• DAS28	✓	✓	✓	✓	✓	✓
• CDAI	✓	✓	✓	✓	✓	✓
• SDAI	✓	✓	✓	✓	✓	✓
• HAQ	✓	✓	✓	✓	✓	✓
• EQ-5D	✓	✓	✓	✓	✓	✓
• mTSS (X-rays of Hands and Feet)	✓			✓		✓
Adverse Events		✓	✓	✓	✓	✓

* Week 104 or last visit

7.6.2 Description of Activities

The following data will be documented (if assessed in routine care):

Physician:

Baseline Visit (Week 0)

1) Informed consent

2) Patient Background

- Patient ID code
- Demographic Data; Birth date or age, Sex (pregnant/lactation), Race, Weight
- Patient status (out-patient, in-patient)
- Duration of illness
- Indication for the current adalimumab therapy
- Complications
- Past illness
- History; Smoking history, History of allergy
- Progression of RA; Severity of RA (Stage), Functional class of RA (Class)

3) Previous treatment of RA; Biologics, DMARDs, Corticosteroids

4) Inclusion / Exclusion criteria

- Inclusion criteria; Age ≥ 16 years old, Duration of RA ≤ 2 years, MTX dose ≥ 12 mg/week, MTX administration ≥ 3 months, DAS28-CRP > 3.2
- Exclusion criteria; Patients who have been previously treated with biologics

5) Current treatment with adalimumab

6) Current concomitant drug treatment

- MTX (From 6 months before adalimumab treatment to current)
 - DMARDs except MTX
-

- Corticosteroids
 - Other concomitant drugs
- 7) Current non-drug treatment for RA
- 8) Current status
- Disease activity (Visual Analog Scale by the physician / VAS evaluation)
 - Joint status (28 joints; tender, swollen)
 - Laboratory values (CRP, ESR)
 - X-rays of Hands and Feet

Follow-up Visits (Week 12, 24, 52, 76, 104, last visit)

- 1) Current treatment with adalimumab
- 2) Current concomitant drug treatment
- MTX
 - DMARDs except MTX
 - Corticosteroids
 - Other concomitant drugs
- 3) Current non-drug treatment for RA
- 4) Current status
- Disease activity (Visual Analog Scale by the physician / VAS evaluation)
 - Joint status (28 joints; tender, swollen)
-

- Laboratory values (CRP, ESR)
- X-rays of Hands and Feet (Week 52, 104)
- (S) AE
- Discontinuation of adalimumab treatment (Reason for discontinuation)

Patient:

Baseline Visit (week 0)

- 1) Informed consent
- 2) Disease activity (Visual Analog Scale by the patient / VAS evaluation)
- 3) HAQ
- 4) EQ-5D

Follow-up Visits (Week 12, 24, 52, 76, 104, last visit)

- 1) Disease activity (Visual Analog Scale by the patient / VAS evaluation)
- 2) HAQ
- 3) EQ-5D

7.6.3 Scales and Scores

The following scores will be derived from the documented data:

1) Disease Activity Score (DAS28):

The DAS28 indicates the severity of the RA. The score varies between 0 and 10, with 10 indicating the highest degree of severity. The DAS28 is calculated from the following

data documented on the physician form:

- A) Joint status: Number of tender joints (each with a maximum of 28)
- B) Joint status: Number of swollen joints (each with a maximum of 28)
- C) ESR (mm/1. h) or CRP (mg/dL)
- D) Patient's assessment of current disease activity (from 0 = inactive to 100 = highly active)

The DAS28 is calculated by means of a validated algorithm.

2) Clinical disease activity index (CDAI):

The CDAI indicates the severity of the RA. The CDAI is calculated from the following data documented on the physician form:

- A) Joint status: Number of tender joints (each with a maximum of 28)
- B) Joint status: Number of swollen joints (each with a maximum of 28)
- C) Patient's assessment of current disease activity (from 0 = inactive to 10 = highly active)
- D) Physician's assessment of current disease activity (from 0 = inactive to 10 = highly active)

The CDAI is calculated by following formula.

$$\text{CDAI} = \text{A) + B) + C) + D)}$$

3) Simplified disease activity index (SDAI):

The SDAI indicates the severity of the RA. The SDAI is calculated from the following data documented on the physician form:

- A) Joint status: Number of tender joints (each with a maximum of 28)
-

- B) Joint status: Number of swollen joints (each with a maximum of 28)
- C) Patient's assessment of current disease activity (from 0 = inactive to 10 = highly active)
- D) Physician's assessment of current disease activity (from 0 = inactive to 10 = highly active)
- E) CRP (mg/dL)

The SDAI is calculated by following formula.

$$\text{SDAI} = \text{A) + B) + C) + D) + E)}$$

4) Health Assessment Questionnaire (HAQ):

The HAQ is the internationally most-used instrument for assessing RA-related functional impairment. The patient has to answer 20 questions concerning impairment in daily activities within the following 8 areas:

- Dressing & Grooming
- Arising
- Eating
- Walking
- Hygiene
- Reach
- Grip
- Activities

Patients assess their functionality over the past week by means of a 4-level scale ranging from 0 (without any difficulty) to 3 (unable to do). The highest (worst) values will be

calculated into a mean value which indicates the degree of functional impairment (HAQ Disability Index: 0-3).

5) EuroQol 5 Dimensions (EQ-5D):

The EQ-5D is a generic (not disease specific) instrument for measuring health-related quality of life. The patient questionnaire includes statements for the following five areas (dimensions):

- Agility & Mobility
- Self-care
- Usual activities
- Pain & Bodily discomfort
- Anxiety & Depression

For each dimension the patient is asked for a three-level assessment of his health on the current day: “no problems” (1), “some problems” (2), “extreme problems” (3). From the possible combinations of the five three-level areas result 241 different health-statuses.

6) X-ray findings of joint damage:

According to the guidelines for X-ray examination, investigators will obtain X-ray images of the both hands and both feet of each patient at baseline and week 52 of treatment. Members of the TSS Academy will score the X-ray images systemically and objectively in terms of bone erosion and joint space narrowing using the mTTS method.

Criteria for evaluation of joint lesions using the mTTS method:

The van der Heijde-modified total Sharp score (mTSS) will be used to score the severity of bone erosion and joint space narrowing shown on the X-ray pictures of the hands and feet. Table 2 shows the scoring criteria⁸⁾.

Table 2. Scoring for Sharp-van der Heijde method

Sharp / van der Heijde method

Erosions:

1 = erosions exist discretely

2 = large erosion

3 = large erosion, extends over the imaginary middle of the bone

5 = collapse completely

Erosion score per joint: sum of erosions with a maximum of 5 per joint for the hands (0-5) and 10 per joint for feet (0-10: max 5 at each site of the joint)

Joint space narrowing:

0 = normal

1 = focal or doubtful

2 = generalized, >50% of the original joint space left

3 = generalized, <50% of the original joint space left or subluxation

4 = bony ankylosis or complete luxation

7.6.4 Study Medication

This is a non-interventional observational study with adalimumab. Adalimumab is used according to the approved label for rheumatoid arthritis and is prescribed by the attending physician. AbbVie GK does not provide any study medication. HUMIRA[®]-injection is available as ready-to-use syringes (injector, pre-filled) and includes 40 mg adalimumab. The recommended dose of adalimumab for adult patients with RA is 40 mg sc every other week.

8.0 Amendments and Updates

Number	Date	Section of Study Protocol	Amendment or Update	Reason
1	31JUL2012		Create New	
2	25APR2013	2.0 Synopsis 7.0 Study objectives	Amendment	1) PMDA requirement 2) Increase the number of patients
3	27NOV2013	2.0 Synopsis 7.0 Study objectives	Amendment	Unachieved registration
4	23FEB2016	9.0 Adverse events 10.0Product complaint	Amendment updated	FDA requirement
5	28MAR2017	7.5 Study Duration	Amendment	Add the day of data analysis and the end of study date due to became clear
6	23AUG2017	7.5 Study Duration	Amendment	Add the day of data analysis and the end of study date due to correct
7	11DEC2017	7.5 Study Duration	Amendment	Change the day of data completion and data analysis

9.0 Adverse Events

9.1.1 Adverse Event Definition and Serious Adverse Event Categories

An adverse event (AE) is defined as any untoward medical occurrence in a patient which does not necessarily have a causal relationship with their treatment. An adverse event can therefore be any unfavorable and unintended sign (including an abnormal laboratory finding), symptom, or disease temporally associated with the use of a medicinal product, whether or not the event is considered causally related to the use of the product. Such an event can result from use of the drug as stipulated in the labeling, as well as from accidental or intentional overdose, drug abuse, or drug withdrawal. Any worsening of a

pre-existing condition or illness is considered an adverse event. If an adverse event meets any of the following criteria, it is considered a **serious adverse event (SAE)**:

Hospitalization or prolongation of hospitalization: An event that results in the admission to the hospital for any length of time. This does not include an emergency room visit or admission to an outpatient facility or an event that occurs while the study subject is hospitalized and prolongs the subject's hospital stay.

Disability: An event that results in a condition that substantially interferes with the activities of daily living of a study subject. Disability is not intended to include experiences of relatively minor medical significance such as headache, nausea, vomiting, diarrhea, influenza, and accidental trauma (e.g., sprained ankle).

Life-Threatening: An event that, in the opinion of the investigator, would have resulted in immediate fatality if medical intervention had not been taken. This does not include an event that would have been fatal if it had occurred in a more severe form.

Death: An event that results in the death of a subject.

Congenital anomaly in the fetus/offspring: An anomaly detected at or after birth that results in fetal loss.

Other medically important conditions: An important medical event that may not be immediately life-threatening or result in death or hospitalization, but based on medical judgment may jeopardize the subject and may require medical or surgical intervention to prevent any of the outcomes listed above (i.e., death of subject, life-threatening, hospitalization, prolongation of hospitalization, congenital anomaly, or persistent or significant disability/incapacity). Examples of such events include allergic bronchospasm requiring intensive treatment in an emergency room or at home, blood dyscrasias or convulsions that do not result in inpatient hospitalization, or the development of drug dependency of drug abuse.

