7.5 Study Duration

- 1) The duration of the whole PMOS is estimated to be about 4 years.

- Study start: September 2012
-

- Recruiting phase: September 2012 - December 2014
 - Data completion: January 2018
 - End of study: The date on which statistical analysis dataset for Clinical Study Report becomes available
 - Data analysis and final report: April 2018 – October 2018
- 2) For each individual patient, the PMOS starts with the enrollment at the beginning of the treatment with adalimumab.
- Observation period
 - 104 weeks (or discontinuation of this study)
 - Discontinuation of this study
 - Patients within 52 weeks into this study: When adalimumab treatment is discontinued.
 - Patients after 52 weeks into this study: When any biologics other than adalimumab is administered.

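### Protocol 9.1.1 contradicts itself on seriousness: read literally, it excludes events that prolong a hospital stay, and its congenital-anomaly wording does not fit its own heading

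*Protocol*

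**What the plan says.** Protocol 9.1.1 lists the criteria that make an adverse event (AE) serious. One is headed "Hospitalization or prolongation of hospitalization". Its definition covers an event leading to admission, of whatever length. The next sentence reads "This does not include an emergency room visit or admission to an outpatient facility or an event that occurs while the study subject is hospitalized"; it continues without a break, so that its last item is "an event that occurs while the study subject is hospitalized and prolongs" the hospital stay.

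Another criterion is headed "Congenital anomaly in the fetus/offspring" and defined as "An anomaly detected at or after birth that results in fetal loss".

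The last criterion in the section, for other medically important conditions, refers back to "any of the outcomes listed above (i.e., death of subject, life-threatening, hospitalization, prolongation of hospitalization", and goes on to name congenital anomaly with no restriction.

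Meeting a criterion has consequences. Protocol 9.4 requires notification within 24 hours, and Protocol 12.0 requires a separate SAE form. SAP 10.2 takes over the seriousness set when CRF data are matched with safety data, and tabulates by it.

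**The concern.** Safety of the combination is a stated objective (Protocol 7.0), and Protocol 9.1.1 holds the only seriousness criteria in either document. If its wording points two ways, two physicians could classify the same prolonged stay differently, each with support in the text. An event serious only because it lengthened a stay, or an anomaly in a live-born child, could be coded non-serious. It would then trigger neither the 24-hour notification nor the SAE form. It could also drop out of the serious columns of the safety tables, but only if AE matching follows Protocol 9.1.1, which the documents do not say.

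**Working it through.** No figure in the plan is to be reproduced here. The check is a comparison of texts, plus one table count and one date calculation.

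**1. Prolongation of hospitalization**

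| Place in Protocol 9.1.1 | Is prolongation serious? |
|---|---|
| Heading of the criterion | Yes, named beside hospitalization |
| Defining sentence | Silent; defines admission only |
| Exclusion sentence | No; third of three items joined by *or* under a single opening negative |
| Outcomes cited under other medically important conditions | Yes, named as already listed |

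Nothing in the exclusion sentence turns its third item back into an inclusion. The criterion as printed therefore removes half of its own heading.

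**2. Congenital anomaly**

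The heading covers fetus and offspring. The definition sets two conditions together: detection no earlier than birth, and fetal loss. The first leaves out anomalies found before birth. The second leaves out anomalies in live-born children. The two conditions hardly fit together, and the later list has neither.

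**3. Does the SAP repair it?**

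No. SAP section 2 defines adverse event and adverse reaction but not seriousness. SAP 10.2 defines a serious AE by the result of matching and does not say which criteria matching applies.

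**4. Which events are exposed?**

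Events that are fatal, life-threatening or disabling, or that cause an admission, remain serious under their own criteria. What is left is events serious only through prolongation, or only as an anomaly outside the narrow wording, and not caught by medical judgement under other medically important conditions. The documents give no counts of AEs, prolonged stays or pregnancies, so the number of such events cannot be computed.

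**5. Which SAP 13.2 tables use seriousness?**

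Counting by title or stated purpose, and letting the site versions of a table inherit its purpose:

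- All: 5.1, 5.1.1 to 5.1.4, 5.2.2, 5.2.3, 5.2.4, 5.3.2, 5.4, 5.4.1, 5.4.2, and 5.5.1.1 to 5.5.1.4. That is 1 + 4 + 3 + 1 + 3 + 4 = 16.
- Covering all AEs: 5.1.1 and 5.3.2 = 2. Covering adverse drug reactions (ADRs) only: 16 − 2 = 14.
- Of the 14, literature analysis only: 5.2.3 and 5.2.4 = 2. Conditional on patient numbers: 5.5.1.1 to 5.5.1.4 = 4. Excluded patients only: 5.1.2 = 1.
- Always produced for the safety set: 14 − 2 − 4 − 1 = 7 ADR tables, plus the 2 AE tables.

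This shows where a misclassified event could appear, not how many there are.

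**6. Can rewording still change data collection?**

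Protocol 7.5 gives "Recruiting phase: September 2012 - December 2014". Taking the last day of that month as the last planned enrolment, 31 December 2014 + 728 days = 28 December 2016. With the SAP 10.1 AE window, 31 December 2014 + 755 days = 24 January 2017. Both dates precede the last protocol amendment (11 December 2017) and SAP version 6.00 (9 April 2018). On the planned dates, follow-up was already over.

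**The case against.** The strongest reply is that this is a drafting slip. The last clause of the exclusion sentence can be read as a misplaced inclusion, and only that reading agrees with both the heading and the later list. That is plausible, but the printed sentence says the reverse and no other text corrects it.

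The second reply is that harm needs a chain of conditions. A physician must follow the exclusion over the heading. The event must be serious on no other ground and must escape medical judgement. For the tables to change, matching must also follow Protocol 9.1.1. This stands, and it limits the severity. So do three safeguards: every AE goes on the CRF (Protocol 12.0), pregnancies have their own 24-hour notification (Protocol 9.5), and some events may also reach the sponsor within 24 hours as device complaints (Protocol 10.1 and 10.2). None of these routes sets seriousness.

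For the anomaly criterion, SAE collection ends when the patient leaves the study (Protocol 9.3). Before week 52 that means stopping adalimumab (Protocol 7.5). Pregnancy or the wish for it is a listed reason for stopping (SAP 11). Many births may therefore fall outside SAE collection under any wording, so this limb is secondary.

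A reader might infer two stronger things that the documents do not support:

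- *That serious events were undercounted.* The criteria used in matching are not shown and no event counts are given. The text establishes a risk of misclassification, not an undercount.
- *That the wording dates from February 2016, so that the share of follow-up after that date measures the exposure.* The log entry for 23 February 2016 names only "9.0 Adverse events 10.0Product complaint" as the sections changed. It does not show that these sentences changed. If they did not, they applied throughout. No person-time percentage measures this defect.

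**Conclusion.** Wrong as written; minor severity. The contradiction over prolongation is certain on the text, and the misfit of the anomaly criterion is equally plain though less important. The possible consequence is missed 24-hour notifications and SAE forms for a narrow set of events. Lower serious AE and ADR counts would follow only on the further assumption that matching applies Protocol 9.1.1. The effect on counts cannot be computed from the documents. The primary endpoint, DAS28 remission at week 52, does not depend on seriousness and is unaffected.

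**What to change.** 1. In Protocol 9.1.1, reconcile both definitions with their headings and with the outcomes cited later in the section. Take prolongation out of the exclusion sentence. Reword the anomaly criterion so that it follows its fetus and offspring heading; deleting the fetal-loss words alone would still leave out anomalies found before birth.
2. In SAP 10.2, add a line stating that AE matching applies the reconciled definition.
3. Because planned follow-up had ended, the rewording cannot alter what was collected. Before the final tables, re-check AEs coded non-serious for prolonged stays, and the known outcomes of reported pregnancies, where existing CRF narratives or safety data allow it. Cover the whole of follow-up, since the text of Section 9.0 before 2016 is not shown. Where the data do not allow the check, state the limitation in the report.

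The third step has to be conditional. Protocol 7.6.2 lists no item for the length or prolongation of a stay, and in-patient status is listed only at week 0, so the documents do not show that prolonged stays can be identified.

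Cost: two sentences in the protocol, one line in the SAP, and a small review of existing data that would grow if sites had to be queried. The downside is possibly slightly more SAEs, some of them reported late.

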9.2 Relationship to Pharmaceutical Product

If an adverse event is occurred in the observation period, the physician will assess the causality of adalimumab with reference to the latest package inserts of adalimumab and concomitant drugs (e.g., methotrexate, corticosteroids). When the causality of an adverse event to the use of a concomitant drug other than adalimumab is suspected, the physician will describe the suspected drug.

The physician will use the following definitions for any adverse event being collected as an endpoint/data point the study and for all serious adverse events, to assess the relationship of the adverse event to the use of the pharmaceutical product:

Probable: An adverse event has a strong temporal relationship to the study drug or recurs on re-challenge, and another etiology is unlikely or significantly less likely.

Possible: An adverse event has a strong temporal relationship to the study drug, and an alternative etiology is equally or less likely compared to the potential relationship to study drug.

Not related: An adverse event is due to an underlying or concurrent illness or effect of another drug is not related to the study drug (e.g., has no temporal relationship to study drug or has a much more likely alternative etiology).

Impossible to judge:

If an investigator's opinion of "not related" to pharmaceutical product is given, **an alternate etiology must be provided by the investigator.**

9.3 Serious Adverse Event Collection Period

Serious adverse events will be reported to AbbVie GK from the time the physician obtains the patient's authorization to use and disclose information (or the patient's informed consent) until the end of the PMOS (week 104 or discontinuation of this study).

9.4 Serious Adverse Event Reporting

In the event of a serious adverse event, and additionally, any non-serious events of malignancy in patient 30 years of age and younger, whether related to adalimumab or not, if applicable - the physician will notify the AbbVie GK contact person (Medical Representative in Japan) within 24 hours of the physician becoming aware of the event.

AbbVie MR will send the AbbVie Pharmacovigilance department identified below.

AbbVie GK [name] Pharmacovigilance Department	
---	--

